#### **6.2.4.** Subgroup Analyses

The effectiveness analyses will also be presented by viral subtype at Screening.

CONFIDENTIAL Page 19 11 July 2016

#### 6.3. SAFETY

#### **6.3.1.** Adverse Events

Adverse events will be mapped to a Medical Dictionary for Regulatory Activities (MedDRA) version 18.0 preferred term and system organ classification. If a subject experiences multiple events that map to a single preferred term, the greatest severity grade and strongest investigator assessment of relation to study medication will be assigned to the preferred term for the appropriate summaries. Should an event have a missing severity or relationship, it will be classified as having the highest severity and/or strongest relationship to study medication. Summaries of treatment-emergent AEs will include any AEs reported beginning with the initiation of study drug on Day 1. The occurrence of treatment-emergent adverse events (TEAEs) will be summarized by treatment group using preferred terms, system organ classifications, and severity. Separate summaries of treatment-emergent serious adverse events, treatment-emergent adverse events related to study drug, and events leading to the discontinuation of study will be generated. All adverse events reported will be listed for individual subjects showing both verbatim and preferred terms. All adverse events that occurred prior to the initiation of study treatment or more than 14 days post-study drug discontinuation will be excluded from the tables but will be included in the listings.

Missing onset dates will be imputed as previously outlined in Section 4.3.5 as required to determine treatment-emergent events.

#### **6.3.2.** Concomitant Medications

Previous and concomitant medications, as well as symptom relief medications recorded on the subject diary, will be coded using the World Health Organization (WHO) dictionary (Version: March, 2015). Concomitant medications will be summarized by frequency of drug classification and generic drug name. Previous and concomitant medications will be presented in a data listing. Symptom relief medications will be presented in a data listing.

#### **6.3.3.** Clinical Laboratory Assessments

Descriptive summaries of the following selected (quantitative) clinical laboratory results will be presented by study visit and treatment group for each age group and overall: ALT, AST, Serum Creatinine, BUN, HGB, Albumin, and Alkaline Phosphatase. Laboratory abnormalities (toxicities) will be graded according to the DAIDS Table for Grading Adverse Events for Adults and Pediatrics (Publish Date: December 2004). The number and percentage of subjects experiencing treatment-emergent graded toxicities will be summarized by treatment group for each age group and overall. Laboratory toxicity shifts from baseline to Day 7 will be summarized by treatment group for each age group and overall.

All laboratory toxicities that occurred before the initiation of study treatment or more than 14 days post study drug discontinuation will be excluded from the tables but will be included in the listings.

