The following procedures/assessments will be performed on Day 14 (+ 3 days). The Day 14 assessments will be performed as a clinic visit, home visit (conducted by a qualified study nurse) or, if either of these options are not possible, by phone call. If conducted by phone, the Day 14 assessments will be limited to interview assessment for the presence of possible influenza-related complications, concomitant medication use and AEs. The subject's parent/ caregiver will be asked to return the completed Subject Diary by mail.

- Body temperature (using the study electronic thermometer via the oral or axillary method).
- Assessment of presence of possible influenza-related complications.

- Vital sign measurements (blood pressure (in children < 2 only if clinically indicated), heart rate, respiration rate).
- Review of the Subject Diary for completeness.
- Determination (and recording in the Subject Diary) of the presence and severity of each of age appropriate symptoms of influenza. Question asked of subjects age 6 years and older, if possible.
- Determination (and recording in the Subject Diary) [with assistance from the subject (if possible)] of the subject's ability to perform usual daily activities.
- Determination (and recording in the Subject Diary) of the subject's appetite and eating patterns assessed as either normal or reduced/abnormal
- Bilateral adequate nasal swab specimen collection for viral culture, quantitative PCR assay and susceptibility to neuraminidase inhibitors.
- Review and recording of concomitant medications.
- Recording of any AEs.
- If previous lab results are abnormal and considered clinically significant by the Investigator or significantly changed from baseline, blood specimen collection for clinical chemistry or clinical hematology tests as specified in Sections 11.2.1 and 11.2.2 may be drawn.
- If previous lab results are abnormal and considered clinically significant by the Investigator or significantly changed from baseline, urine collection for urinalysis may be completed.

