10.2.2.6. Early Withdrawal

For subjects who withdraw before the Day 7 assessment, the following procedures/assessments will be performed at an Early Withdrawal visit, where possible. Assessments will be performed as a clinic visit or home visit (conducted by a qualified study nurse). For subjects who withdraw between the Day 7 and day 14 assessments, a phone assessment will be performed, where possible. A phone assessment will be limited to interview assessment for the presence of possible influenza-related complications and AEs. The subject's parent/caregiver will be asked to return the completed Subject Diary by mail.

- Urine pregnancy test (females of childbearing potential only).
- Body temperature (using the study electronic thermometer via the oral or axillary method).
- If previous lab results are abnormal and considered clinically significant by the Investigator or significantly changed from baseline, blood specimen collection for clinical chemistry or clinical hematology tests as specified in Sections 11.2.1 and 11.2.2 may be drawn

- If previous lab results are abnormal and considered clinically significant by the Investigator or significantly changed from baseline, urine collection for urinalysis may be completed
- Assessment of presence of possible influenza-related complications.
- Vital sign measurements (blood pressure (in children < 2 only if clinically indicated), heart rate, respiration rate).
- Review of the Subject Diary for completeness.
- Determination (and recording in the Subject Diary) of the presence and severity of each of the age appropriate symptoms of influenza. Questions asked of subjects age 6 years and older, if possible.
- Determination (and recording in the Subject Diary) [with assistance from the subject (if possible)] of the subject's ability to perform usual daily activities.
- Determination (and recording in the Subject Diary) of the subject's appetite and eating patterns assessed as either normal or reduced/abnormal
- Bilateral adequate nasal swab specimen collection for viral culture, quantitative PCR assay and susceptibility to neuraminidase inhibitors.
- Review and recording of concomitant medications.
- Recording of any AEs.

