11.2.1. Clinical Chemistry Profiles

Clinical chemistry profiles will include a Chemistry 20 panel (includes sodium, potassium, chloride, total CO₂ [bicarbonate], creatinine, glucose, urea nitrogen, albumin, total calcium, total magnesium, phosphorus, alkaline phosphatase, alanine aminotransferase (ALT), aspartate aminotransferase (AST), total bilirubin, direct bilirubin, lactate dehydrogenase (LDH), total protein, total creatine kinase, and uric acid).

Blood samples for clinical chemistry profiles will be collected at Baseline and at the Day 7 follow-up assessment. Clinically significant results should be reported as AEs.

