13.9. Safety Analyses

Adverse Events will be mapped to a Medical Dictionary for Regulatory Activities (MedDRA)-preferred term and system organ classification. The occurrence of treatment-emergent AEs (TEAEs) will be summarized by age group and treatment group using MedDRA-preferred terms, system organ classifications, and severity. All AEs will be listed for individual subjects showing both verbatim and preferred terms. Separate summaries of treatment-emergent SAEs and AEs related to study drug will be generated.

Descriptive summaries of vital signs and clinical laboratory results will be presented by age group, treatment group and study visit. Laboratory abnormalities will be graded according to the DAIDS Table for Grading Adverse Events for Adults and Pediatrics (Publish Date: December 2004 Clarification, 2009, see Appendix 1). The number and percentage of subjects experiencing treatment-emergent graded toxicities will be summarized by age group and treatment group. Laboratory toxicity shifts from baseline to post-baseline assessments will be summarized by age group and treatment group.

Previous and concomitant medications will be mapped to a WHO preferred term and drug classification. The number and percent of subjects taking concomitant medications will be summarized using preferred terms and drug classifications.

The number and percent of subjects experiencing influenza related complications will be summarized by age group and treatment group.

Subject disposition will be presented for all subjects. The number of subjects who completed the study and discontinued from the study will be provided. The reasons for early discontinuation also will be presented.

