# 2.2. SCHEDULE OF EVENTS/STUDY VISITS

Assessments	Screening 	Baseline  Pre-Dose	Day 1  Post-Dose	Day 3 	Day 7 (±2 day)	Day 14  (±3 day)	End of Study Early Withdrawal 
Informed Consent	X						
Inclusion/Exclusion Criteria	X						
Pregnancy Test (Urine) 	X				X		X
Medical History	X						
Body Temperature 	X	X	X	X	X	X	X
Physical Exam		X					
Influenza-related complications (IRC) checklist 		X		X	X	X	X
Vital Signs 		X		X	X	X	X
Concomitant Medications Review 	X	X	X	X	X	X	X
Clinical Chemistries and Hematology 		X			X		X
Urinalysis 		X			X		X
Assessment of influenza symptoms/ activities of daily living/ eating habits 		X	X	X	X	X	X
Subject Diary Completion/ Review 		X	X	X	X	X	X
Nasal swabs for Virology Analysis 		X		X	X	X	X
Study Drug Administration 		X					
Serum sample for influenza antibody analysis 		X			X		
Pharmacokinetic (PK) Sampling 			X				
Adverse Events			X	X	X	X 	$X^{16}$

Study Measurements and Visit Schedule Figure Legend on Next Page

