# 4.3.6. By Study Visit Displays

When data are collected serially over time, individual data presentations may include by-visit displays. For these presentations, visits will be presented according to the nominal visit as obtained from the CRF or laboratory data. If assessments are collected with multiple dates or times within a given visit, the result closest to the scheduled visit date will be used for summary presentations. If two measurements have the same distance to the expected date, the earlier value will be used. If a subject has multiple non-missing values on the same date, then the last one is used, as determined by the time collected, if available.

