# 7. CHANGES IN THE PLANNED ANALYSES

An analysis of the number of doses of antipyretic medications will be prepared.

There are no further changes anticipated to the protocol specified analyses. Should any more deviations occur, these changes will be fully described in the Clinical and Statistical Report.

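### SAP 6.3.3 limits the laboratory shift tables to Day 7 where Protocol 13.9 plans shifts to post-baseline assessments, and SAP 7 does not declare the change

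*SAP*

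**What the plan says.** Protocol 13.9 plans: "Laboratory toxicity shifts from baseline to post-baseline assessments will be summarized by age group and treatment group". SAP 6.3.3 plans: "Laboratory toxicity shifts from baseline to Day 7 will be summarized by treatment group for each age group and overall". SAP 7 adds an analysis of antipyretic doses and then says: "There are no further changes anticipated to the protocol specified analyses".

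Three further provisions decide which results reach the shift tables.

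- **Visit assignment.** SAP 4.3.6 presents data by the nominal visit taken from the CRF or laboratory data. Where a visit holds several dated results, "the result closest to the scheduled visit date will be used for summary presentations".
- **Sampling in the protocol.** Section 11.2.1 says: "Blood samples for clinical chemistry profiles will be collected at Baseline and at the Day 7 follow-up assessment". Sections 11.2.2 and 11.2.3 say the same for hematology and urinalysis. Day 14 tests are optional. Section 10.2.2.5 opens the provision with "If previous lab results are abnormal and considered clinically significant by the Investigator or significantly changed from baseline, blood specimen collection for clinical chemistry", and the same condition applies at Early Withdrawal (section 10.2.2.6; Table 1, footnote 17). That visit itself is conditional: "the following procedures/assessments will be performed at an Early Withdrawal visit, where possible".
- **Sampling in the SAP.** In SAP 2.2, the row "Clinical Chemistries and Hematology" is marked at Baseline, Day 7 and End of Study/Early Withdrawal, without the protocol's condition. It has no mark at Day 14.

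SAP 6.3.3 also plans a separate count of treatment-emergent graded toxicities (Table 14.3.5.2). SAP 4.3.8 defines these as a rise of at least one grade at any post-baseline visit up to 14 days after the last dose.

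**The concern.** Laboratory results are part of the primary endpoint (Protocol 7.1.1; SAP 2.1), and the shift tables are the only specified display that sets a child's baseline grade against a later grade. The SAP narrows that display without declaring it. The table titles in SAP 10 do not mention Day 7, so a reader of the report could take the tables as covering all post-baseline results.

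The results left out are not a random subset. They arise because a child left early or because an earlier result was abnormal or had changed. The quantitative summaries in SAP 6.3.3 cover only seven analytes: ALT, AST, creatinine, BUN, hemoglobin, albumin and alkaline phosphatase. For neutrophils, creatine kinase and the rest, the shift tables and Table 14.3.5.2 are the only planned laboratory summaries.

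**Working it through.** The plan gives no figure to reproduce. The check compares the texts and counts days with the SAP's own study-day formula.

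**1. Which results can enter the shift tables as SAP 6.3.3 is written?**

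| Result | Foreseen in | In the Day 7 shift? | In Table 14.3.5.2 if the grade rose? |
|---|---|---|---|
| Day 7, nominal | Protocol 11.2; SAP 2.2 | Yes (closest to schedule if several) | Yes |
| Early Withdrawal, before Day 7 | Protocol 10.2.2.6 (conditional); SAP 2.2 | No | Yes |
| Unscheduled, own label | Protocol Table 1, footnote 16 (further follow-up) | No | Yes, within 14 days of last dose |
| Day 14 repeat | Protocol 10.2.2.5 (conditional) | No | Yes, within 14 days of last dose |

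The exclusion follows the visit label. A repeat filed under the Day 7 visit can still be selected if it is closest to the scheduled date.

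**2. Where do the two wordings differ?** Protocol Table 1, section 10.2.2.4 and section 11.2 all make Day 7 the routine post-dose laboratory visit. One sentence in Protocol 10.1 says final study visit instead, but it stands alone. A completer with a Day 7 sample and no repeat has the same shift under either document.

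A completer with a Day 14 repeat normally had it because an earlier result was abnormal or changed. The scheduled post-dose result that could trigger it is Day 7, which is already in the table. That child's shift changes only if the repeat is worse than Day 7.

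The clearest loss is a child who withdraws before Day 7 and has a post-dose sample. That child has no post-baseline entry in any shift table.

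**3. Does the treatment-emergent window catch what the shift tables miss?** Study day = event date − date of Day 1 + 1.

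- Peramivir: single dose on Day 1, so the window ends on Day 1 + 14 = Day 15.
- Oseltamivir, last dose on Day 5: the window ends on Day 5 + 14 = Day 19.
- Protocol Day 14 visit (+3 days): Days 14 to 17.

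Early Withdrawal samples before Day 7 fall inside the window in both arms. Day 14 repeats on oseltamivir all fall inside. On peramivir, repeats on Days 14 and 15 fall inside, while those on Days 16 and 17 go to the listings only.

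**4. How much does one child weigh?** The neonatal cohort is up to 10 children, so one child is at least 1/10 = 10%. Protocol 13.4 gives up to 140 children, about 117 on peramivir, which leaves about 140 − 117 = 23 on oseltamivir, so one child there is about 1/23 = 4%. These figures show what a single omission means. They do not estimate how many omissions there will be.

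**The case against.** The case against is substantial, and most of it stands.

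- **Worsening is not hidden.** A reader might infer that the worst grade disappears from the report. It does not. Table 14.3.5.2 counts a rise at any post-baseline visit in the window, and the listings give every result. Clinically significant results are reported as adverse events (Protocol 11.2) and tabulated by greatest severity (SAP 6.3.1). The SAP does not say whether Table 14.3.5.2 shows maximum grade, and no table shells are supplied.
- **The protocol does not ask for worst grade.** Section 13.9 speaks of post-baseline assessments. It mentions neither the worst grade nor unscheduled results.
- **No count of affected children is supported.** Assuming that 5–10% withdraw early, one might infer that 0.05 × 140 = 7 to 0.10 × 140 = 14 children are lost from the shift tables. The rate is an assumption. Moreover, Early Withdrawal tests under the current protocol require an earlier abnormal or changed result, and before Day 7 the only scheduled earlier result is baseline. Many such children would have no post-dose sample, so no shift definition could include them.
- **Transient abnormalities before Day 7 are conjecture.** No sample is scheduled between dosing and Day 7. Protocol 11.2 says which laboratory analyzes hospitalized children's samples, not that extra ones are taken. The 21.4% rate of decreased neutrophil count (Protocol 5.3.2.1) comes from another study and says nothing about off-schedule results here.
- **Different counts in the two tables are no defect.** One is an incidence over a window and the other a fixed-visit shift.
- **The analysis is descriptive** (Protocol 13.3), so no test is affected.

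None of this removes the undeclared mismatch, or the fact that the SAP's own schedule marks tests at Early Withdrawal that its shift tables cannot use.

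**Conclusion.** The point holds in a limited form. SAP 6.3.3 narrows a primary-safety display from what Protocol 13.9 describes, and SAP 7 does not say so. By the nominal-visit rule, results labelled Early Withdrawal, unscheduled or Day 14 stay out of the three shift tables.

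The loss is confined to that display. Most completers are unaffected, and grade increases within 14 days of the last dose are still counted and listed. Results beyond that window, such as a peramivir repeat on Day 16 or 17, are in the listings only. How many children are affected cannot be computed from the documents.

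This rests on applying SAP 4.3.6 as written and on samples carrying their own visit labels. The missing Day 14 mark in SAP 2.2 may mean that the SAP, with a page dated 11 July 2016, was not updated to protocol version 6.0. That would explain part of the gap and is itself a reason to revise.

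**What to change.** In SAP 6.3.3, define the shift as baseline grade to worst post-baseline grade within the treatment-emergent window of SAP 4.3.8. Use all scheduled, unscheduled, Early Withdrawal and Day 14 results, and state that the closest-to-schedule rule does not apply to this derivation. Keep the Day 7 shift as a second panel and label both panels in the titles of Tables 14.3.5.3.1 to 14.3.5.3.3. Record in SAP 7 that worst grade is the chosen way of carrying out Protocol 13.9. State also whether Table 14.3.5.2 shows maximum grade, and bring the laboratory rows of SAP 2.2 into line with the current protocol.

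The cost is one extra derivation, one extra panel and a few sentences. No new data are needed. Peramivir repeats on Days 16 and 17 would remain in the listings only, and a footnote should say so.

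If the sponsor prefers Day 7 alone, the minimum is to declare and justify it in SAP 7 and name Day 7 in the table titles. That resolves the undeclared change but does not bring the omitted results into the tables.

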# **6.3.4.** Other Safety Analyses

Descriptive summaries of vital signs will be presented by study visit and treatment group for each age group and overall.

All abnormal physical examination findings will be summarized by study visit and treatment group for each age group and overall.

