- Subjects 28 days to < 13 years of age will receive a weight-based dose administered as a capsule or oral suspension (twice daily for 5 days).

Note, as of the approval of amendment 3, no additional subjects will be randomized to receive oseltamivir.

Criteria for evaluation:

Safety:

• Safety will be evaluated through assessments of Adverse Events (AEs), laboratory analyses (clinical chemistry, hematology and urinalysis), vital signs, and physical examinations. A review and summary of safety utilizing all collected assessments will be performed by a Data Safety Monitoring Committee (DSMC) after each influenza season as outlined in the DSMC charter.

Pharmacokinetic:

• Plasma peramivir concentrations will be measured by a validated liquid chromatography-tandem mass spectrometry (LC/MS-MS) assay. Concentrations will be utilized in determination of population pharmacokinetic parameters.

Effectiveness:

- **Clinical:** Time to resolution of fever; time to resolution of influenza symptoms (per the age appropriate symptoms);
- **Virologic:** Viral shedding; virus susceptibility.

Statistical methods:

Sample Size:

The study is designed to evaluate the safety and pharmacokinetics of IV administration of peramivir in pediatric subjects with influenza. The sample size is adequate to evaluate these objectives. Descriptive comparison between peramivir and oseltamivir treated subjects will be performed where possible. Formal hypothesis testing will not be performed.

Safety:

Qualitative analyses will be performed for AE type, frequency and severity, as well as vital sign absolute values, clinical laboratory absolute values, and physical examination findings and their respective changes from Baseline for all subjects.

Pharmacokinetics:

Plasma concentrations and covariates of interest will be evaluated in a meta-population analysis using mixed effect modeling techniques to estimate population pharmacokinetic parameters in each age group and to identify pharmacokinetically-relevant covariates. Data from the completed pediatric study 0918T0633 of IV peramivir in Japan will be included in this analysis.

Effectiveness:

Clinical and virologic endpoints will be summarized using descriptive statistics.

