# Change from Baseline

Change from baseline for a given endpoint is defined as the Study Day X value minus the Baseline Value.

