#### 6. STATISTICAL METHODS

Descriptive statistical methods will be used to summarize the data from this study. Data will be summarized by treatment group, age group, and study day/time, if appropriate. Unless stated otherwise, the term "descriptive statistics" refers to number of subjects (n), mean, median, standard deviation (SD), minimum, and maximum for continuous data and frequencies and percentages for categorical data. The term "treatment group" refers to randomized treatment assignment: single dose peramivir IV or oseltamivir BID for 5 days. The term "age group" refers to the following: 28 days - < 2 years,  $\ge$  2 years - < 7 years,  $\ge$  7 years - < 13 years, and  $\ge$  13 years - < 18 years. All data collected during the study will be included in data listings. Unless otherwise noted, the data will be sorted first by treatment group, age group, subject number, and then by date within each subject number.

The statistical analyses will be conducted with the SAS® software package version 9.2 or higher. All analyses will be subject to formal verification procedures. Specifically, results will be verified utilizing independent programming prior to issuance of the draft statistical report. All documents will be verified by the lead statistician to ensure accuracy and consistency of analyses.

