The development of any post treatment genotypic changes in neuraminidase and hemagglutinin will be assessed by comparison of sequences from baseline and last positive post-treatment virus samples. These analyses will be presented overall and by age group, treatment group and viral subtype.

The number and percentage of subjects experiencing influenza related complications will be summarized by age group and overall by complication preferred term and treatment group.

The number of doses of antipyretic medications, as recorded in the subject diary, taken throughout the study and by study day will be summarized by age group and overall by treatment group.

The change in daily activities will be summarized each day by treatment group for each age group and overall.

The shift in the assessment of appetite and eating patterns from baseline to each day will be summarized by treatment group for each age group and overall.

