Table 14.2.3.1.2	Summary of Changes $\log_{10}$ Tissue Culture Infective Dose 50 (TCID 50 /mL) by Study Visit and Viral Sub-Type; Intent-to-Treat Infected Population
Table 14.2.3.2.1	Summary of Viral Shedding by Study Visit; Intent-to-Treat Infected Population
Table 14.2.3.2.2	Summary of Viral Shedding by Study Visit and Viral Sub-Type; Intent-to-Treat Infected Population
Table 14.2.3.3.1	Summary of RT-PCR Result by Study Visit; Intent-to-Treat Infected Population
Table 14.2.3.3.2	Summary of RT-PCR Result by Study Visit and Viral Sub-Type; Intent-to-Treat Infected Population
Table 14.2.3.4	Change of Influenza Virus Susceptibility to Neuraminidase Inhibitors by Viral Subtype; Intent-to-Treat Infected Population
Table 14.2.4	Summary of Influenza-Related Complications; Intent-to-Treat Infected Population

Output Number	Output Title
Table 14.2.5	Number of Doses of Antipyretic Medications; Intent-to-Treat Infected Population
Table 14.2.6	Summary of Subject-Rated Assessment of Ability to Perform Daily Activities; Intent-to-Treat Infected Population
Table 14.2.7	Summary of Assessment of Appetite and Eating Patterns; ITTI Population
Table 14.3.1.1	Treatment-Emergent Adverse Events by System Organ Classification, Preferred Term and Greatest Severity; Safety Population
Table 14.3.1.2	Treatment-Emergent Adverse Events Possibly, Probably, or Definitely Related to Study Drug by System Organ Classification and Preferred Term; Safety Population
Table 14.3.1.3	Treatment-Emergent Serious Adverse Events by System Organ Classification and Preferred Term; Safety Population
Table 14.3.1.4	Treatment-Emergent Adverse Events Leading to the Discontinuation of Study by System Organ Classification and Preferred Term; Safety Population
Table 14.3.5.1	Summary of Select Laboratory Values by Study Visit; Safety Population
Table 14.3.5.2	Graded Laboratory Toxicities; Safety Population
Table 14.3.5.3.1	Laboratory Shifts from Baseline: Chemistry; Safety Population
Table 14.3.5.3.2	Laboratory Shifts from Baseline: Hematology; Safety Population
Table 14.3.5.3.3	Laboratory Shifts from Baseline: Urinalysis; Safety Population
Table 14.3.6	Summary of Vital Signs by Study Visit; Safety Population
Table 14.3.7	Abnormal Physical Examinations; Safety Population
Table 14.3.8	Concomitant Medications by Generic Name and Drug Classification; Safety Population

Output Number	Output Title

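### Vital signs, part of the primary safety endpoint, are promised changes from Baseline in the synopsis, but Protocol 13.9 and the SAP plan by-visit values only.

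*SAP*

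**What the plan says.** Protocol 7.1.1 names vital signs as a primary endpoint component, alongside adverse events, laboratory analyses and physical examinations. The safety paragraph of the synopsis, under statistical methods, describes qualitative analyses of adverse events "as well as vital sign absolute values, clinical laboratory absolute values, and physical examination findings and their respective changes from Baseline for all subjects".

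Protocol 13.9 is narrower: "Descriptive summaries of vital signs and clinical laboratory results will be presented by age group, treatment group and study visit". SAP 6.3.4 follows it: "Descriptive summaries of vital signs will be presented by study visit and treatment group for each age group and overall". The matching output, Table 14.3.6, is titled "Summary of Vital Signs by Study Visit; Safety Population".

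SAP 4.3.8 does hold a general definition: "Change from baseline for a given endpoint is defined as the Study Day X value minus the Baseline Value". In SAP Section 6, the term for descriptive statistics "refers to number of subjects (n), mean, median, standard deviation (SD), minimum, and maximum for continuous data".

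Laboratory data are treated differently. SAP 6.3.3 plans by-visit summaries of seven analytes (ALT, AST, creatinine, BUN, hemoglobin, albumin, alkaline phosphatase), and adds: "Laboratory toxicity shifts from baseline to Day 7 will be summarized by treatment group for each age group and overall". SAP 4.3.8 defines a treatment-emergent laboratory abnormality as a rise of one grade or more over Baseline.

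**The concern.** A safety reader wants to know how far each child's pulse, respiration or blood pressure moved, and whether any child moved a long way. A table of visit values answers neither question, because it does not link a child's later value to that child's own Baseline. The trial is descriptive throughout, so its summary tables are the main presentation of its primary endpoint.

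By-visit columns may also describe different children. Protocol 10.2.2.5 allows Day 14 by phone when no visit is possible, and a phone contact yields no vital signs. Blood pressure under age 2 is taken only when clinically indicated.

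A related problem affects laboratory data. Under Protocol 6.0, Day 14 and Early Withdrawal laboratory repeats are optional and follow only results that were abnormal and judged clinically significant, or that had changed significantly from Baseline. SAP 4.3.6 groups results by nominal visit, so a selected set of children could appear as an ordinary visit mean.

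**Working it through.** **1. Is change from Baseline implied for vital signs?** Where the SAP intends a change or shift, it says so:
- SAP 6.2.2 plans change from Baseline in viral titer.
- It also says "The change in daily activities will be summarized each day by treatment group for each age group and overall", and plans a shift summary for appetite.
- SAP 6.3.3 plans laboratory grade shifts.
- The titles of the viral titer and laboratory shift tables in SAP Section 10 carry the same language.

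SAP 6.3.4 and the title of Table 14.3.6 have no such wording, and no safety text applies the SAP 4.3.8 definition to vital signs. A programmer working from SAP Section 6 and 6.3.4 would produce six statistics of the values at each visit and nothing paired.

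**2. What visit columns give with full attendance.** If the same n children are measured at both visits, the n of the change is n and the mean change is the difference of the two visit means. That recovers 2 of the 6 statistics. The median, SD, minimum and maximum of change depend on which Baseline value belongs with which later value, so 6 - 2 = 4 cannot be recovered.

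For the SD, assume equal SD s at both visits and within-child correlation r:

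SD of change = s × sqrt(2(1 - r))

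| r (assumed) | SD of change |
|---|---|
| 0 | 1.41s |
| 0.3 | 1.18s |
| 0.5 | 1.00s |
| 0.7 | 0.77s |
| 0.9 | 0.45s |

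The same visit columns fit every row. The documents give neither s nor r.

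**3. What they give with incomplete attendance.** Let k of n children have no Day 14 value. Let D be the Baseline mean of the children measured at Day 14 minus that of the children not measured. The Baseline mean of those measured minus the Baseline mean of all n is (k/n) × D. Hence

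Day 14 mean (measured) - Baseline mean (all n) = mean paired change + (k/n) × D.

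Using planned cohort maxima:
- Birth to <28 days, n = 10: k = 1, 3, 5 gives 0.10D, 0.30D, 0.50D.
- 28 days to <2 years, n = 20: k = 1, 5, 10 gives 0.05D, 0.25D, 0.50D.

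The values of k are illustrative, and neither k nor D is in the documents. The extra term is zero if every child is measured or if those missed have the same Baseline mean.

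**4. Laboratory data.** Protocol 13.9, SAP 6.3.3 and Tables 14.3.5.2 and 14.3.5.3.1 to 14.3.5.3.3 supply Baseline-referenced grades and shifts. What is missing is numeric change in the seven analytes of Table 14.3.5.1.

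**The case against.** - **The synopsis line is loose.** It speaks of qualitative analyses and also promises changes in physical examination findings, although the only scheduled full examination is at Baseline. It does not specify a six-statistic change table, and for laboratory data grade shifts arguably meet it. This stands, and it limits the point to vital signs. For them the plan offers neither a numeric nor a qualitative comparison with Baseline.
- **Temperature is covered.** Protocol 11.3 counts it as a vital sign, and the SAP analyzes time to fever resolution from each child's diary in the infected population. This stands, so the gap is in pulse, respiration and blood pressure.
- **Adverse events are a safeguard.** Any sign that worsens can be an adverse event, and the DAIDS table grades hypertension, hypotension, arrhythmia and respiratory distress. Clinically relevant worsening can therefore reach Table 14.3.1.1. A reader might infer that deterioration would be invisible, and the documents do not support that. What stays unsummarized is movement not reported as an event.
- **Change would be hard to interpret.** No vital signs are scheduled after dosing on Day 1, and the next are on Day 3, so change includes recovery from influenza. This stands. Visit means have the same limitation.
- **An undeclared departure.** SAP Section 7 lists no change on this point, and a reader might infer that the SAP dropped a commitment silently. The documents do not support that. The mismatch lies first inside the protocol, between the synopsis and 13.9, and the SAP follows 13.9. The SAP is dated July 2016 and gives neonates 12 mg/kg where Protocol 6.0 gives 8 mg/kg, so it appears to predate that version.

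**Conclusion.** The gap is real but minor. A commitment on a primary endpoint component is not delivered for pulse, respiration and blood pressure, and four of the SAP's own six statistics for their change cannot be rebuilt from the planned table. That count assumes only that the same children are measured at both visits. The SD range rests on an assumed correlation of 0 to 0.9 and equal visit SDs. The attendance effect cannot be sized and may be zero.

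A reader might go further and say that laboratory values are also summarized by visit only, or that the safety conclusions would be biased. The first is wrong, given the graded toxicities and shift tables. The second has no support, since neither k nor D is given.

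The harm is limited: nothing is formally tested, SAP Section 9 requires each continuous summary to show its non-missing n, Listing 16.2.8.3 gives individual vital signs, and clinically significant laboratory results are adverse events. The change is worth making because it gives a better summary from data already collected.

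**What to change.** In SAP 6.3.4 and Table 14.3.6, add within-child change from Baseline at each follow-up visit, using the SAP 4.3.8 definition, with the paired n, by age group and treatment. For blood pressure under age 2, report how many children were measured at both visits, since pairs may be few. State the same in Protocol 13.9 so that it agrees with the synopsis.

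Optionally, add numeric change from Baseline to Day 7 in Table 14.3.5.1. Limit the by-visit laboratory means to Baseline and Day 7, and list the triggered Day 14 and Early Withdrawal repeats separately.

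Deleting the change wording from the synopsis would remove the inconsistency but would not supply the better summary.

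The cost is some SAP and protocol wording and a few extra columns in one table, or two with the laboratory option. No new data are needed: Protocol 11.3 already schedules vital signs at Baseline and each follow-up visit.
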